## 8.0 Subject Population

This is a single site study that will be conducted at the University of Cincinnati Medical Center (Cincinnati, OH). Up to 10 subjects will be enrolled and receive a headset for monitoring.

### 8.1 Inclusion Criteria

Subjects who meet all of the following inclusion criteria will be considered candidates for study enrollment:

1. Male or female patients age 22 years and older
2. Diagnostic head CT scan within 24 hours of primary spontaneous ICH symptom onset
3. ICH >3mL and <90mL, as measured by the ABC method
4. Signed written informed consent by study subject or, if subject is unable, by subject's next of kin or legal guardian
5. Willingness and ability to comply with schedule for study procedures

### 8.2 Exclusion Criteria

All subjects meeting any of the following criteria will be excluded from this study:

1. Female patients who are pregnant or lactating
2. Patients with any history of seizure or seizure at stroke onset
3. Presence or history of any other condition or finding that, in the investigator's opinion, makes the patient unsuitable as a candidate for the SENSE device monitoring or study participation or may confound the outcome of the study
4. Any intraventricular hemorrhage on the diagnostic (pre-enrollment) CT with planned placement of an intraventricular catheter
5. Secondary cause of ICH suspected (e.g., arteriovenous malformation, cavernoma, aneurysm, hemorrhagic transformation ischemic stroke, venous sinus thrombosis, trauma)
6. Planned withdrawal of care within 24 hours of enrollment
7. Planned surgical evacuation within 24 hours of enrollment
8. Current participation in a medical or surgical interventional clinical trial
9. Presence of subdural, epidural or aneurysmal subarachnoid hemorrhage on diagnostic scan

10. Planned continued use or prescribed use during the study of medications that, in the investigator's best clinical judgment, are known or suspected to lower the seizure threshold
11. Planned continued use of medications that, in the investigator's best clinical judgment, could increase the chances for subsequent uncontrolled hemorrhage
12. Planned or current use of continuous EEG monitoring

## 9.0 Study Procedures

Subjects enrolled in this study will complete the study as outlined below. All tests and measurements should be obtained in accordance with the procedures specified in this protocol. If it is not possible to perform a measurement or examination due to the individual's condition, the reason for not performing the test or measurement should be documented on the source documents.

ICH patients will be screened at the enrolling center based on the inclusion and exclusion criteria for the study. Those not meeting criteria will simply be clinically managed per standard of care and will not be enrolled in the study. Those who meet eligibility criteria will be approached for possible consent and enrollment. This must be done quickly as hemorrhage expansion occurs early in the clinical course; and the subject should be enrolled within 2 hours of the diagnostic CT, whenever practicable.

A consent process must be executed for all subjects entered in the study. Obtunded and aphasic patients are not automatically excluded from the study. If the next of kin or legal guardian (i.e., the individual legally empowered in the state where the consent is obtained) cannot provide consent, entry into the study will not proceed.

After enrollment, routine clinical management will ensue in the ED, hospital ward or ICU as appropriate.

[NOTE: The data from SENSE monitoring in this first-in-man study will be shielded from clinical staff and will in no way inform clinical management.]

### 9.1 Study Duration

The study duration is a total of up to 8 weeks which includes up to 72 ( $\pm 12$ ) hours for SENSE device and CT scan monitoring, and a follow-up phone call at 6 ( $\pm 2$ ) weeks.

### 9.2 Examination Schedule

The following examination schedule will be followed from screening through 6 ( $\pm 2$ ) weeks post-enrollment:

- **Diagnosis:** CT Scan 1 – standard of care; diagnostic head CT scan within 24 hours of symptom onset.

- **First Study CT:** CT Scan 2 – study CT; first study CT scan as soon as practicable after informed consent, followed by SENSE monitoring. Place SENSE device on subject's head within 15 minutes of completion of the first CT scan or as soon as practicable, with continuous SENSE monitoring until the SENSE device is removed to perform the 12-hour CT scan. If there is a delay in obtaining the first study CT scan, SENSE monitoring may begin after informed consent and before the first study CT scan to capture possible HE.
- **12 Hours:** CT Scan 3 – standard of care; CT scan 12 ( $\pm 6$ ) hours after first study CT scan, followed by continuous or intermittent SENSE monitoring. For continuous SENSE monitoring, replace SENSE device on the subject's head within 15 minutes, or as soon as practicable, after completion of the 12-hour CT scan and obtain continuous SENSE measurements until the SENSE device is removed to perform the 72-hour CT scan. If continuous SENSE monitoring is temporarily suspended or for any reason (e.g., unscheduled CT scan, EEG, patient care), resume continuous monitoring as soon as practicable. For intermittent monitoring, the SENSE device will be placed on the patient for a minimum of 22 minutes every 6 ( $\pm 1$ ) hours until the 72-hour CT scan is obtained. A final SENSE measurement will be completed within 15 minutes before or after the 72-hour CT scan.
- **72 Hours:** CT Scan 4 – study CT; end of study CT scan 72 ( $\pm 12$ ) hours after first study CT scan.
- **Unscheduled:** Unscheduled CT scan(s) may be obtained as needed throughout the study per standard of care as warranted by the treating team. Any head CT performed for clinical deterioration as standard of care between the first and 72 hour study CTs will be collected and analyzed. If SENSE monitoring has been temporarily suspended or is being performed intermittently, obtain a SENSE measurement within 15 minutes before or after the unscheduled CT scan whenever practicable, following the procedures above.
- **6 weeks:** Phone call with patient or surrogate to capture the presence or absence any adverse events that may have emerged after completion of the 72-hour SENSE device measurement period.

All eligible subjects must have the diagnostic head CT scan demonstrating hemorrhage performed within 24 hours of symptom onset.

Eligible subjects or legally authorized representative will be approached for enrollment after screening is completed and before the first study CT and SENSE measurements are obtained. After obtaining informed consent to participate in the study, a first study head CT will be performed to establish the hemorrhage volume; and the SENSE device will be placed on the subject within 15 minutes of this CT, or as soon as practicable, for initiation of monitoring. This repeat CT (after the diagnostic CT) is necessary since HE occurs

early in the clinical course, and the hemorrhage volume may have changed between the diagnostic CT and placement of the SENSE monitor. If there is a delay in completing the first study head CT, SENSE monitoring may be started after informed consent and before the first study head CT to obtain SENSE measurements during the time that HE is most likely to occur.

A standard of care head CT to evaluate for HE will be performed at 12 ( $\pm 6$ ) hours after the first study head CT. Finally, a study head CT will be performed at 72 ( $\pm 12$ ) hours to evaluate cerebral edema. Any head CT performed for clinical deterioration as standard of care between the first and 72 hour study CT will also be collected and analyzed. A SENSE scan will be performed ~~within 1 hour before or~~ within 15 minutes, or as soon as practicable, before or after each CT scan, for the purpose of obtaining SENSE measurements at the same time as the CT scan to compare the output from the SENSE device with the CT scans.

SENSE monitoring should be obtained continuously after the first study CT scan and until the SENSE headset is removed for the 12 hour CT scan. After the 12 hour CT scan, SENSE monitoring should be performed continuously or intermittently until the SENSE headset is removed for the 72 hour CT scan. If intermittent monitoring is requested by the subject or the subject's physician at any time after the 12 hour CT scan, the SENSE device will be placed on the patient for a minimum of 22 minutes every 6 ( $\pm 1$ ) hours until the 72-hour CT scan is obtained. A final SENSE measurement will be completed 15 minutes before or after the 72-hour CT scan.

### 9.3 SENSE Device Monitoring Procedure

The device will be used according to the written Instructions for Use provided by the Sponsor. The device will emit and analyze signals of 40 seconds once every 10 minutes for up to a maximum of 72 ( $\pm 12$ ) hours, effectively minimizing the amount of RF radiation to which the subject is exposed while providing essentially continuous monitoring from a clinical point of view. This corresponds to a duty cycle (DC) of about 7%.

If the subject's condition is such that a SENSE device measurement cannot be obtained, the measurement may be omitted at the investigator's discretion; and the omission should be documented in the source documents.

The user interface requires the researcher to input the subject ID and headset ID so that the results can be entered into a database either via upload or manually. The research personnel will also sync the headset with the control box. Once these steps are completed, the research personnel can activate the device by hitting "Start Monitoring." The software will provide error messages if any required fields are blank.

Once activated, the device scans the subject according to the schedule selected per protocol. Before each scan, the device will run a diagnostic to ensure that all components are functioning normally. Data will be collected after each scan for subsequent analysis and correlation with clinical and imaging data.

The processing control unit will store the results from each subject's scans in a file on the device. If the subject ID is changed, the device will start a new file.

When the SENSE device is placed on the subject's head, two small ink dots will be marked on the head corresponding to a known location on the device to allow for the device to be removed and replaced consistently throughout testing. If the SENSE device is removed to perform the CT or SENSE monitoring is temporarily suspended for any reason (including whenever a routine EEG is performed) during continuous SENSE monitoring, the SENSE device will be replaced; and SENSE monitoring will resume within 15 minutes, or as soon as practicable, after each CT scan or other reason for suspension is finished. For intermittent SENSE monitoring, the SENSE device will be replaced and SENSE measurements obtained at 6 ( $\pm$ 1) hour intervals. A SENSE measurement obtained within 15 minutes ~~of before or after~~ each CT scan, or as soon as practicable thereafter, will be used for comparison with the corresponding CT scan for data analysis. The purpose of obtaining SENSE measurements at the same time as the CT scan is to compare the output from the SENSE device with the CT scans.

Subjects requiring continuous EEG monitoring or other care that precludes placement of the SENSE device will have SENSE monitoring discontinued; and the subject will be terminated from the study according to the procedures described in Section 9.10, Early Termination if SENSE monitoring cannot be resumed during the remainder of the study.

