In summary, these *in vivo* porcine frontal lobe ICH model experiments demonstrated that the prototype device detected the increase in the received power after ICH was induced in the pig brain. The results were consistent with the *in vitro* data at 400 MHz. However, a greater increase in received power (and a smaller pig-to-pig variation in  $P_R$ ) was observed at higher frequencies in the 750–1000 MHz range. One of the limitations of the *in vivo* work was the fact that when the antennas were not aligned collinearly to the ICH,  $P_R$  increases were much smaller. While this was not unexpected, it pointed out the need for a multi-dimensional array.

Further experiments were conducted using a two-dimension and three-dimension array design. By adding antenna in a third axis, it was theorized that ICH location could be more precisely pinpointed. Subsequently, a 9-antenna array was developed to enhance the ability of the device to detect intracranial hemorrhage anywhere in the brain. Using

---

 Unpublished data on file, 2014. Research funded by University of Cincinnati Technology Commercialization Accelerator award.

the porcine intracranial hemorrhage model, blood was detected in different areas of the brain, at varying volumes; and, the impact of multiple hemorrhages within the same brain was studied.

*In Vivo* Testing of the 9-antenna array: For the *in vivo* experimentation, different types of experiments were performed (see Table 1). Each experiment was conducted on a separate pig (i.e. a total of 8 pigs). In the first four experiments (#1-4), the right frontal white matter was infused with 3 mL of blood. In the next two experiments (#5-6), there were two sequential infusions into the right frontal white matter to mimic hemorrhage expansion. In the final two experiments (#7-8), blood was infused sequentially in the left parietal and right frontal white matter to determine if two separate hemorrhages could be detected. For all of these experiments, the SENSE device ran continuously for 6-8 hours.

Table 1 – In vivo porcine ICH infusion study designs

Experiment #	Infusion #1 Location	Infusion #1 Volume (mL)	Infusion #2 Location	Infusion #2 Volume (mL)
1,2,3,4	Right Frontal	3	N/A	N/A
5	Right Frontal	2	Right Frontal	1
6	Right Frontal	1	Right Frontal	2
7	Left Parietal	1	Right Frontal	2
8	Left Parietal	2	Right Frontal	1

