## **6.0 Endpoints**

The primary endpoint for this early feasibility study is the correlation of the SENSE signal with CT changes over time.

Secondary endpoints will include the ability to process collected data in a manner that allows application and use of the SENSE device in a clinical environment and a preliminary estimate of the safety of the device when used in a clinical setting. Serious, unexpected adverse events will be recorded. Epileptic seizures will be an adverse event of special interest and recorded regardless of serious or unexpected status.

Qualitative information regarding device tolerability and compatibility with ICU workflow will be obtained from study subjects and ICU staff.

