### 10.5 Efficacy Criteria

**Scheduled Exam Intervals:** The change in received power ( $P_R$ ) measured by the SENSE device will be calculated and the accuracy of the SENSE algorithm will be tested for the SENSE measurements that correspond with the first, 12 hour, and 72 hour CT scans; and  $P_R$  will be compared to the hemorrhage volume on the corresponding CT scan. The change in  $P_R$  and CT hemorrhage volumes from the first study CT to 12 hours and from 12 hours to 72 hours will also be evaluated. Data will be summarized using descriptive statistics.

**Unscheduled CT Scans:** For any unscheduled CT scan that has a corresponding SENSE measurement, the SENSE  $P_R$  will be calculated and the accuracy of the SENSE algorithm will be tested; and the comparison to the hemorrhage volumes on the corresponding CT scan will be evaluated.

Although the sample size is small, the sensitivity and specificity of the  $P_R$  for monitoring changes in ICH will be estimated and evaluated for suitability as an outcome measure for determining the sample size for the pivotal study design.

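### One SENSE value per CT, chosen only by time, forces at least one analysed change in received power across a headset re-placement, and the plan never estimates the repositioning error

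*Combined protocol and SAP*

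**What the plan says.** Section 6.0 states: "The primary endpoint for this early feasibility study is the correlation of the SENSE signal with CT changes over time". Section 10.5 adds that the change in received power and in "CT hemorrhage volumes from the first study CT to 12 hours and from 12 hours to 72 hours will also be evaluated".

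The SENSE value that represents each CT is defined by time. Section 9.3 (and 7.0 in the same terms) refers to a measurement within 15 minutes: "each CT scan, or as soon as practicable thereafter, will be used for comparison with the corresponding CT scan for data analysis". Section 9.2 allows either side of the scan: "before or after each CT scan, for the purpose of obtaining SENSE measurements at the same time as the CT scan". For the last CT it says: "A final SENSE measurement will be completed 15 minutes before or after the 72-hour CT scan". No section says which headset placement the value must come from.

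On wear, section 9.2 says: "SENSE monitoring should be obtained continuously after the first study CT scan and until the SENSE headset is removed for the 12 hour CT scan". The headset is then replaced. From there to 72 h, monitoring is either continuous or intermittent; intermittent means a fresh placement of at least 22 minutes every 6 (±1) hours. In continuous mode the device scans once every 10 minutes and stores every result (section 9.3).

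The control on re-placement is the pair of ink dots, used "to allow for the device to be removed and replaced consistently throughout testing". Section 9.5.2 also asks for head movements that may affect headset position to be recorded on the CRF. No analysis rule uses either.

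**The concern.** A change in received power is meant to reflect a change inside the head. If its two values come from different placements, it also contains whatever difference in headset position remains after lining up the dots. Such an error, if independent of the change in hemorrhage volume, pulls the correlation towards zero. The same values would feed the sensitivity and specificity estimates that section 10.5 considers for sizing the pivotal study.

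Two features make this worth raising in a small feasibility study. The crossing follows from using one value per CT, so careful conduct at the site cannot remove it. And for at least the first interval the scans needed to avoid it are normally already in the device file.

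**Working it through.** The documents give no sample size, power or repositioning figure on this point, so there is no stated number to reproduce.

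**1. Count the re-placements inside each analysed change.** Call the placement after the first study CT P1, the one after the 12 h CT P2, and any placement after the 72 h CT P3. This assumes removal for each CT, as section 9.2 schedules; 7.0 and 9.3 word removal as conditional. With the first value taken after the first CT (P1):

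| 12 h value | 72 h value | Re-placements crossed, first CT to 12 h | Re-placements crossed, 12 h to 72 h |
|---|---|---|---|
| before removal (P1) | before removal (P2) | 0 | 1 |
| before removal (P1) | after (P3) | 0 | 2 |
| after (P2) | before removal (P2) | 1 | 0 |
| after (P2) | after (P3) | 1 | 1 |

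No row is 0 and 0. If monitoring starts before the first CT and that value is used, the first interval crosses 1 or 2, so those four combinations fail as well. The table assumes continuous wear; suspensions or intermittent monitoring only add crossings.

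**2. Check that same-placement scans exist.** One scan per 10 minutes is 6 per hour.
- First CT to 12 h: 12 × 6 = 72 scans (6 × 6 = 36 to 18 × 6 = 108 across the ±6 h window), in one placement if there is no suspension.
- 12 h to 72 h: 60 × 6 = 360 scans. The windows give (60 − 18) × 6 = 252 to (84 − 6) × 6 = 468. These are in one placement only with uninterrupted continuous wear.

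**3. Illustrate the effect on the correlation.** Let r be the SD that re-placement adds to a change, divided by the SD of the change without it. If the error is additive and independent of everything else, the correlation is multiplied by 1/√(1 + r²). The values of r are assumed.

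| r | Factor | A correlation of 0.70 becomes |
|---|---|---|
| 0.25 | 1/√1.0625 = 0.97 | 0.68 |
| 0.5 | 1/√1.25 = 0.89 | 0.63 |
| 1.0 | 1/√2 = 0.71 | 0.49 |
| 1.5 | 1/√3.25 = 0.55 | 0.39 |

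If each placement carries an independent offset with SD τ, then r = √2·τ/SD. The factor applies to the interval that crosses. If both intervals were pooled with equal SDs and numbers, and only one crossed, the factor would be 1/√(1 + r²/2): 0.98, 0.94, 0.82 and 0.69.

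**4. Allow two values at 12 h.** The first interval becomes P1 to P1 and, with the 72 h value taken before removal, the second becomes P2 to P2. A constant placement offset cancels in both, so the r² term drops out.

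**The case against.** **The animal evidence is indirect.** A reader might infer from section 2.1 that re-placing the headset has been shown to shift received power. It has not. The smaller increases "when the antennas were not aligned collinearly to the ICH" concern where the bleed lay relative to the axis of a two-antenna prototype. The same section gives this as the reason for moving to a multi-dimensional array, and the 9-antenna array is the device used here. Position sensitivity is plausible; a re-placement shift for this array is not documented. This objection stands.

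**The size is not anchored.** At r = 0.25 the loss is negligible. Sampling error is also large: an observed correlation of 0.70 from 10 subjects with one change each has a Fisher 95% interval of tanh(0.867 ± 1.96/√7), about 0.13 to 0.92. This stands too, and is a reason to measure the error rather than assume it.

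**Same-placement data are not always available.** A reader might infer that they exist for every interval. They are assured only from first CT to 12 h without suspension. Under intermittent monitoring each value in the second interval is a new placement.

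**The rule is not open-ended.** It has a 15-minute window, relaxed only to as soon as feasible. Tracked-change marks leave the exact wording in 7.0 and 9.3 partly unclear. The count does not depend on this: the window limits time, not placement, and 9.2 clearly allows either side.

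**Handling may lie elsewhere.** The Instructions for Use or the proprietary algorithm might deal with re-placement, and the stored scans permit a within-placement analysis later. Nothing in the protocol says that either is done.

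**The study is descriptive.** It has up to 10 subjects, no success criterion and no separate SAP, so no error rate is at stake. This limits the weight of the point but does not answer it.

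**Conclusion.** The point holds in a bounded form. Given scheduled removal at 12 h and one SENSE value per CT, at least one of the two changes in section 10.5 crosses a re-placement. Any repositioning error therefore enters the primary correlation, and the plan has no estimate of it. That conclusion rests on counting placements and needs no assumption about size.

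The size is unknown. The range 0.97 to 0.55 is illustrative and should not be read as a forecast for this trial. Nor do the documents support saying that re-placement will produce false detections: that depends on the algorithm, which section 2.1 describes as using a limit above the maximum drift observed.

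The noise is only partly avoidable. Same-placement changes still carry system drift and headset shift during wear, more so over the roughly 60 hours of the second interval. The benefit is a cleaner exploratory estimate for pivotal planning. That makes this a recommended change to the analysis rule, not a threat to the study.

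**What to change.** Add to sections 9.3 and 10.5, for intervals with uninterrupted continuous wear:

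- First CT to 12 h: first valid scan after placement following the first study CT, against the last valid scan before removal for the 12 h CT.
- 12 h to 72 h, only if monitoring stays continuous: first valid scan after re-placement, against the last valid scan before removal for the 72 h CT.
- Define a valid scan before the data are examined.
- For each subject with scans on both sides of the 12 h CT, report the difference between the last scan before removal and the first after re-placement. Its spread estimates the SD that re-placement adds to a change, with scan-to-scan noise and any real change over that gap included.
- Show separately the changes that cross a placement (intermittent monitoring, suspensions) and pairs outside 15 minutes.

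The comparison of received power with volume at each single CT, also in 10.5, is not corrected by this; state which 12 h value it uses.

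Cost: a short paragraph of wording and a small amount of extra analysis. No added scans, visits or subjects are needed, because continuous monitoring already stores the data. The rule cannot rescue the second interval for subjects on intermittent monitoring.
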